13.2 Clinical Data Records.....	39
13.3 Record Retention	40
13.4 Discontinuation of the Study	40
13.5 Publication Policy	40
13.6 Study Audits	40
14. REFERENCES.....	41
APPENDICES	43
APPENDIX 1: STUDY GOVERNANCE	43
APPENDIX 2: THE INFLUENZA PATIENT-REPORTED OUTCOME INSTRUMENT (FLU-PRO® PLUS).....	44
APPENDIX 3: DAILY SURVEY	46
APPENDIX 4: WHO ORDINAL SCALE FOR CLINICAL IMPROVEMENT	48

ABBREVIATIONS AND TERMS

Term	Definition
ADR	Adverse drug reaction
AE	Adverse event
AUC	Area under the curve
BMGF	Bill and Melinda Gates Foundation
BMI	Body mass index
C _{max}	Maximum concentration
COVID-19	Coronavirus disease
DAIDS	Division of Allergy and Infectious Diseases
DSMB	Data Safety and Monitoring Committee
EC	Ethics Committee
EFD	Embryofoetal development
EOS	End of study
eCRF	Electronic case report form
FLU-PRO©	InFLUenza Patient-Reported Outcome
FSH	Follicle stimulating hormone
GCP	Good Clinical Practice
GD	Gestation day
HIV	Human immunodeficiency virus
HREC	Human Research Ethics Committee
IATA	International Air Transport Association
ICF	Informed consent form
IMP	Investigational medicinal product
IRB	Institutional Review Board
LRTI	Lower respiratory tract infection
MedDRA	Medical Dictionary for Regulatory Activities
NHC	β-D-N4-hydroxycytidine
NHC-TP	NHC 5'-triphosphate
PPE	Personal protective equipment
RHD	Recommended human dose
RT-PCR	Reverse transcriptase polymerase chain reaction
SAE	Serious adverse event
SAHPRA	South African Health Products Regulatory Authority
SAP	Statistical Analysis Plan
SARS-CoV-2	Severe acute respiratory syndrome coronavirus 2
SOE	Schedule of Events
SpO ₂	Oxygen saturation
SmPC	Summary of Product Characteristics
SRT	Safety Review Team
T _{max}	Time to maximum concentration
TB	Tuberculosis
WHO	World Health Organization
WHO-DD	WHO Drug Dictionary

SYNOPSIS

Title	A randomised, multi-centre, double-blind, Phase 3 study to observe the effectiveness, safety and tolerability of molnupiravir compared to placebo administered orally to high-risk adult outpatients with mild COVID-19 receiving local standard of care in South Africa
Short Title	COTeT
Rationale	
Recurring waves and outbreaks of COVID-19 driven by the highly transmissible Delta (B.1.617.2) variant and most recently by the Omicron variant first described in South Africa, are exacerbating the global public health crisis. Vaccines have substantially reduced the morbidity and mortality rates in those infected with SARS-CoV-2, and several therapeutic agents, including steroids, have been shown to impact on severe disease¹⁻³. However, individuals who have been infected or vaccinated still run the risk of recurrent infection. These infections are often symptomatic, with occasional severe morbidity and even mortality in those with similar risk factors for severe disease to those without immunity.
 
Several oral, injectable and infusion agents have been tested for use as early treatment, and several promising oral agents have recently emerged. These include fluvoxamine, molnupiravir and nirmatrelvir, and all have an impact on hospitalization and severe outcomes. Multiple other agents are being investigated. While study design varied for these new agents, all appear to have maximum impact if administered soon after symptom onset (within 3-5 days), and for several days. This aligns with the current understanding of the development of SARS-CoV-2 infection: an initial viral infection and dissemination phase is followed by an immunological phase (during which immunomodulation contributes significantly) in certain high-risk patients with associated severe morbidity and mortality. Current thinking is that new agents play a role in early disease by limiting viral replication and potentially preventing or limiting the subsequent immunological phase. The effectiveness of these agents relies on early presentation of patients to a relevant health care facility, rapid confirmation of SARS-CoV-2 infection, and prompt initiation of therapy.
 
South Africa, like many countries, has endured several waves of SARS-CoV-2, with some estimates suggesting that 80% of the population have been infected. Excess mortality due to the virus is recorded at just over 300 000 since the first cases in March 2020⁴, in a population of 50 million. Currently, only 48% of the population have been vaccinated (68% in those over 60 years)⁵. Accurate comparisons with elsewhere on the continent, or even with high income countries are difficult, although there are some suggestions that South African mortality is particularly high. This may be due to the very high levels of obesity and diabetes, both significant risk factors for poor COVID-19 outcomes, as well as high levels of HIV, also somewhat associated with poorer outcomes^{6,7}. Access to agents with a demonstrated ability to impact hospitalisation and severe outcomes related to COVID-19 will have clear benefits in the South African context but is limited by the time to registration of new drugs, or caveats attached to the use and monitoring of unregistered products through the Section 21 mechanism.
 
Rapid access to molnupiravir in South Africa will be facilitated for a large number of COVID-19 patients through this Phase 3 clinical trial while awaiting registration applications and procedures. The LumiraDx™ point of care diagnostic platform for diagnosis of SARS-CoV-2 infection through antigen detection, will enable rapid confirmation of COVID-19 in patients with recent onset of symptoms and mild disease. Patients who meet the enrolment criteria will have same-day initiation of a five-day treatment course of molnupiravir, and will be followed to monitor tolerability, adverse


	drug reactions, effectiveness through time to resolution of symptoms and progression to severe disease (requiring hospitalisation and/or resulting in death), and adherence.
Design	
This is a multi-centre, double-blind, Phase 3 study to observe the effectiveness, safety, and tolerability of molnupiravir 800 mg administered 12-hourly for five days to adult patients with mild COVID-19 at the time of enrolment who are at risk of progression to severe disease, compared to a placebo.
 
Patients with recent onset of COVID-19 symptoms will be screened to assess eligibility for enrolment. Confirmation of SARS-CoV-2 infection will be performed through rapid antigen detection using the LumiraDx™ point of care diagnostic platform. Eligible patients will be enrolled and will be randomised in a 1:1 manner to start treatment with either molnupiravir or a placebo on the same day. Patients will record their symptoms (through a self-administered questionnaire) and self-observed vital signs daily for 10 days from the time of enrolment and will be contacted by study team personnel on Days 3, 6 and 10 to monitor their well-being. Adverse event and concomitant medication data will be collected. A final end-of-study follow-up visit will be conducted on Day 29.
 
An independent Data and Safety Monitoring Board (DSMB) will be convened for this study with expertise in COVID-19 or respiratory viruses, and emerging epidemics. The purpose of the DSMB is to monitor the study for safety and operational futility.
 
In addition to the usual, regular, required reporting to SAHPRA, we anticipate that additional reporting may be required, noting the severity of the 3rd and 4th waves, the level of "breakthrough" infections in the context of high background comorbidities, and the urgent interest in this class of drugs.

Population	
Adults ≥50 years of age with self-reported symptoms of COVID-19 for no more than five days prior to screening, and who test positive for SARS-CoV-2 antigen on the day of screening or have a documented positive SARS-CoV-2 RT-PCR within 2 days prior to screening, and who are at risk of progression to severe disease, will be enrolled.
 
The following eligibility criteria will be used to select study participants.
 
Inclusion criteria:
 
1. Able and willing to provide written or electronic informed consent prior to any study-specific procedure.2. Age ≥50 at the time of signing the informed consent form.3. Women of reproductive potential must have a negative pregnancy test at screening and be using a highly effective method of contraception. Highly effective methods of contraception include:
a. Hormonal methods of contraception for at least 14 days prior to screening (including oral contraceptive pills, injectables, or implants)b. Intrauterine devices from at least 7 days prior to screening (including hormone-releasing, and non-hormone-releasing devices)c. Bilateral tubal ligationd. Engaging exclusively single-sex relationshipse. Sexual abstinence4. A male participant must wear a condom when engaging in any activity that allows for passage of ejaculate to another while taking the investigational product. Male participants should also be advised of the benefit for a female partner to use a highly effective method of contraception as condom may break or leak5. Self-reported symptoms of COVID-19 with onset no more than five days prior to screening informed consent including at least one of, fever or chills, cough, sore throat, rhinorrhoea or rhinitis or sinusitis, shortness of breath, headache, myalgia, new onset anosmia or ageusia, nausea, diarrhoea, or extreme fatigue,

	
or other symptoms recognized in local and international guidelines as typical of mild COVID-19.
 
6. SARS-CoV-2 infection confirmed through a positive LumiraDx™ rapid antigen test on the day of screening or a positive RT-PCR within two days prior to screening.
 
7. Participant is at high risk for progression to severe COVID-19, this defined as either:
 
Age ≥ 50 with at least one of the following background or medical conditions: diabetes mellitus, obesity ($BMI \geq 30 \text{ kg/m}^2$), hypertension, HIV, or active or previous TB.Age ≥ 65 
8. Participant agrees to comply with study procedures, including the completion of a daily diary for 10 days from the time of enrolment, and to be available for study contacts and visits.
 
Exclusion criteria:
 
Pregnant or breastfeeding women, or women planning/desiring to become pregnant during the 28 days following enrolment into the study.Duration of self-reported symptoms of COVID-19 for more than five days prior to screening.Signs of respiratory distress or severe disease prior to enrolment, including:
respiratory rate >24 breaths/min$\text{SpO}_2 <95\%$ in room airheart rate ≥ 120 bpmabnormal mental statusinability to walk due to COVID-19 symptomsinability to talk in full sentences due to COVID-19 symptomsa requirement for hospitalisation.Inability/unlikely to be in the study area for the duration of the 28-day follow-up period.Inability to tolerate oral medications.Any surgical or medical condition which might significantly alter the absorption, distribution, metabolism, or excretion of drugs, or which may jeopardize the safety of the patient or the objectives of the study. The Investigator should make this determination in consideration of the volunteer's medical history.The volunteer is assessed to be clinically unstable in the Investigator's opinion.Participation in another investigational study involving an investigational product within 30 days, or 5 half-lives, whichever is longer, prior to screening.Personnel (e.g., investigator, sub-investigator, research assistant, pharmacist, study coordinator or anyone mentioned in the delegation log) directly involved in the conduct of the study.Any physical, mental, or social condition, drug/alcohol use, history of illness or laboratory abnormality that, in the Investigator's judgment, might jeopardise the safety of the patient in the context of this study, or might interfere with study procedures or the ability of the subject to adhere to and complete the study. The Investigator should make this determination in consideration of the volunteer's medical history. 
Volunteers may be re-screened if they are found not to have COVID-19 at the time of the initial screening, but develop a further, and distinct, acute illness suggestive of COVID-19 at a later stage.

Investigational Medicinal Product	Molnupiravir 800 mg 12-hourly or placebo administered orally for five days.

Objectives and Endpoints	Primary Objectives	Primary Endpoints
	
• To evaluate the effectiveness of molnupiravir compared to placebo in preventing severe disease progression in adults with mild COVID-19• To evaluate the safety of molnupiravir in adults with mild COVID-19 
Secondary Objectives
 
• To facilitate same-day COVID-19 diagnosis and treatment initiation in adults with mild COVID-19 and comorbid conditions• To assess the tolerability of molnupiravir in adults with mild COVID-19• To describe time to symptom resolution in adults with mild COVID-19 treated with molnupiravir compared to placebo• To evaluate maximum COVID-19 disease severity in adults treated with molnupiravir compared to placebo• To evaluate the relationship between effectiveness of molnupiravir and time between onset of symptoms and initiation of treatment• To describe adherence to a 5-day course of molnupiravir in adults with mild COVID-19• To describe the utilisation of health care services by adults with mild COVID-19 treated with molnupiravir compared to placebo• To report the incidence and outcome of pregnancies in female participants who received molnupiravir	
• Combination of incidence of COVID-19-related hospitalisation (≥ 24 hours of care in a hospital or similar acute care facility) and COVID-19-related mortality to Day 29• Adverse events (including serious adverse events and adverse drug reactions)• Self-assessed vital signs to Day 10 
Secondary Endpoints
 
• Proportion of enrolled patients for whom diagnosis and same day treatment initiation was facilitated through use of a LumiraDx™ rapid antigen test• Severity of adverse events• Adverse event-related study drug discontinuations• Time to sustained resolution of symptoms as reported in the Flu-PRO® Plus• Maximum score on the WHO Clinical Progression Scale from Day 1 to Day 29• Number of days from symptom onset to initiation of treatment• Incidence of hospitalisation (≥ 24 hours of care in a hospital or similar acute care facility) and/or death to Day 29 in patients with co-morbid conditions• Time to sustained resolution of symptoms as reported in the Flu-PRO® Plus• Maximum score on the WHO Clinical Progression Scale from Day 1 to Day 29• Proportion of patients completing the course of molnupiravir as prescribed• Rate of hospital, emergency facility, clinic, health care practitioner or home visits to Day 29• Incidence of pregnancy in female participants to Day 29• 20-week gestational age ultrasound findings• Pregnancy complications• Pregnancy outcome• Infant wellbeing to three months of age

	
Exploratory Objectives
 
• To describe the proportions of eligible patients from different sites of screening• To describe the proportion of women failing screening due to pregnancy• To describe COVID-19 disease severity in adults who receive molnupiravir with different at-risk indicators• To describe the symptoms of COVID-19 in male compared to female adult participants• To describe COVID-19 disease severity in vaccinated compared to unvaccinated adults who receive molnupiravir
Sample Size	4000 patients will be enrolled into this study (2000 per treatment arm).
Duration	29 days per participant.

1. SCHEDULE OF EVENTS

Procedure / assessment	Screening/ Enrolment	Treatment and Follow-Up (including self-quarantine as required in accordance with local guidelines)							EOS Day 29 (±3) ^b
	Day 0 ^a	Day 1-2	Day 3	Day 4-5	Day 6	Day 7-9	Day 10		
Informed consent	X								
Demography	X								
Duration of COVID-19 symptoms	X								
Pregnancy and lactation status ^c	X								
Urine pregnancy test ^d	X								
LumiraDx™ SARS-CoV-2 Ag testing ^e	X								
Point of Care HIV test ^f									
Past and current medical conditions (including COVID-19 vaccination status)	X								
Concomitant medications, including contraception	X		X		X			X	X
Physical examination, including weight and height ^g	X								X
Vital signs (temp., pulse, BP, RR, SpO2) ^h	X								X
Eligibility criteria	X								
WHO Clinical Progression Scale ⁱ	X		X		X			X	X
Study treatment ^j		X	X	X					
Patient reported vital signs (temp., pulse and SpO2) ^k		X	X	X	X	X	X		
Completion of daily survey and FLU-PRO® Plus questionnaire ^l		X	X	X	X	X	X		X
Adverse event review ^m			X		X			X	X
Return of unused IMP and empty containers									X ^m
Contact with study staff ⁿ	X		X		X			X	

EOS: end of study; temp.: body temperature; BP: blood pressure; RR: respiratory rate; SpO2: oxygen saturation; WHO: World Health Organization.

Note: Participants who stop study product should continue study participation off study product with continued evaluations as per the schedule of activities. The reason for study product discontinuation should be recorded.

^a A window period of -1 day may apply in cases where COVID-19 symptoms have not already been present for 5 days at the time of screening. Screening/enrolment (Day 0) and initiation of study treatment and follow-up (Day 1) are anticipated to occur on the same day for most participants.

^b For participants who are hospitalized at the time of the scheduled Day 29 visit, the EOS visit will be approximately 3 days after discharge.

^c Female participants only.

^d Urine pregnancy test for women of reproductive potential only.

- ^e Participants with same-day LumiraDx SARS-CoV-2 Ag from another vendor or a laboratory confirmation of an RT-PCR positive for SARS-CoV-2 within 2 days prior to screening will not require an additional rapid antigen test.
- ^f Optional HIV point of care testing will be offered to participants at screening. Newly diagnosed patients will be referred appropriately for care.
- ^g An abbreviated, symptom-directed physical examination including at least a general examination and chest auscultation will be performed. Height will be measured at screening only.
- ^h Body temperature will be measured. Pulse, RR and SpO₂ will be measured after at least 5 minutes resting.
- ⁱ To be performed via telephone call or text/direct messaging or web-based conference, or in person as necessary. For the Day 3, 6 and 10 contact sessions, a window period of ± 1 days is permitted. This window period will also apply to the assessment of the WHO Clinical Progression Scale score by the study team personnel, and the review of adverse event and concomitant medication data to be performed during these contact sessions.
- ^j Molnupiravir 800 mg will be taken approximately 12-hourly, with a glass of water, with or without food, for five days (10 doses).
- ^k The Day 1 assessments will be performed by enrolled participants under observation of the study personnel. Assessments will be recorded utilizing a mobile phone/tablet application, or other device, or diary, or during a telephonic or in person interaction with the site personnel. Assessments may be performed by study personnel if an in-person visit is conducted after completion of the quarantine period.
- ^l The FLU-PRO[®] Plus questionnaire and daily survey will be recorded daily for 10 days by participant utilizing a mobile phone/tablet application or diary. The daily survey will consist of the FLU-PRO[®] Plus Global Additional Daily Diary Items (related to general well-being, overall severity of symptoms, and ability to perform usual daily activities) as well as other general daily diary questions related to study drug administration, recording of vital signs and SpO₂ measurements, review of concomitant medications, and information related to possible adverse events.
- ^m Serious adverse events, adverse events resulting in treatment discontinuation, and all other AEs, including those judged by the site Investigator to be related to the administered treatment regimens.
- ⁿ Or anytime from Day 6 if an earlier contact visit takes place.

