
Objectives
 
 • To facilitate same-day COVID-19 diagnosis and treatment initiation in adults with mild COVID-19 and comorbid conditions • To assess the tolerability of molnupiravir in adults with mild COVID-19 • To describe time to symptom resolution in adults with mild COVID-19 treated with molnupiravir compared to placebo • To evaluate maximum COVID-19 disease severity in adults treated with molnupiravir compared to placebo • To evaluate the relationship between effectiveness of molnupiravir and time between onset of symptoms and initiation of treatment • To describe adherence to a 5-day course of molnupiravir in adults with mild COVID-19 • To evaluate the utilisation of health care services by adults with mild COVID-19 treated with molnupiravir compared to placebo 	
Endpoints
 
 • Proportion of enrolled patients for whom diagnosis and same day treatment initiation was facilitated through use of a LumiraDx™ rapid antigen test • Severity of adverse events • Adverse event-related study drug discontinuations • Time to sustained resolution of symptoms as reported in the Flu-PRO® Plus • Maximum score on the WHO Clinical Progression Scale from Day 1 to Day 29 • Number of days from symptom onset to initiation of treatment • Incidence of hospitalisation ((≥24 hours of care in a hospital or similar acute care facility) and/or death to Day 29 in patients with co-morbid conditions • Time to sustained resolution of symptoms as reported in the Flu-PRO® Plus • Maximum score on the WHO Clinical Progression Scale from Day 1 to Day 29 • Proportion of patients completing the course of molnupiravir as prescribed • Rate of hospital, emergency facility, clinic, health care practitioner or home visits to Day 29

To report the incidence and outcome of pregnancies in female participants who received molnupiravir	
Incidence of pregnancy in female participants to Day 2920-week gestational age ultrasound findingsPregnancy complicationsPregnancy outcomeInfant wellbeing to three months of age
Exploratory	
Objectives	

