4. STUDY DESIGN

4.1 Overall Design

This is a multi-centre, double-blind, phase 3 study to observe the effectiveness, safety, and tolerability of molnupiravir 800 mg administered 12-hourly for five days in adult patients with mild COVID-19 at the time of enrolment, who are at risk of progression to severe disease, compared to a placebo.

Patients with recent onset of COVID-19 symptoms will be screened to assess eligibility for enrolment. Confirmation of SARS-CoV-2 infection will be performed through rapid antigen detection using the LumiraDx™ point of care diagnostic platform. Approximately 4000 eligible patients will be enrolled and will be randomised in a 1:1 manner to start treatment with either molnupiravir or a placebo on the same day. Patients will record their symptoms (through a self-administered questionnaire) and self-observed vital signs daily for 10 days from the time of enrolment and will be contacted by study team personnel on Days 3, 6 and 10 to monitor their well-being. Adverse event and concomitant medication data will be collected. A final end-of-study follow-up visit will be conducted on Day 29.

An independent Data and Safety Monitoring Board (DSMB) will be convened for this study with expertise in COVID-19 or respiratory viruses, and emerging epidemics. The purpose of the DSMB is to monitor the study for safety and operational futility.

In addition to the usual, regular, required reporting to SAHPRA, we anticipate that additional reporting will be required by the Clinical Trials Committee, noting the severity of the 3rd and 4th waves, the level of “breakthrough” infections in the context of high background comorbidities, and the urgent interest in this class of drugs.

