8.3 Efficacy Assessments

8.3.1 Patient Reported Outcomes

Participants will be asked to complete the following surveys during the study:

- The FLU-PRO[®] Plus questionnaire¹⁹⁻²¹ to assess the symptomatic extent of their illness (Appendix 2)
- The daily survey (Appendix 3) that includes:

- The FLU-PRO[®] Plus Global Additional Daily Diary Items (related to general well-being, overall severity of symptoms, and ability to perform usual daily activities)
- General daily diary items (related to study drug administration, recording of vital signs and SpO₂ measurements, review of concomitant medications, and information related to possible adverse events).

These surveys will be completed electronically or using a participant diary. Participants will be contacted via telephone call or text/direct messaging or web-based conference on day 3/6/10 by a staff member to confirm any AE occurrence, general well-being and update the WHO clinical progression scale. The participants will fill in the surveys daily themselves for 10 days, these will be collected at EOS or if electronically captured, before then.

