APPENDIX 2: THE INFLUENZA PATIENT-REPORTED OUTCOME INSTRUMENT (FLU-PRO[®] Plus)

To be completed on D1-10, and D28:

FLU-PRO Plus[®]

People experience viral respiratory tract infections in different ways. We would like to know about the symptoms you have been experiencing during the past 24 hours. For each symptom, please mark one box under the response that best matches your experience. Mark the "Not at all" box, if you did not have that symptom in the past 24 hours.

What time is it? _____ AM / PM (please circle)

Please rate the extent to which you had each symptom during the past 24 hours.

	Not at all	A little bit	Somewhat	Quite a bit	Very much
Runny or dripping nose					
Congested or stuffy nose					
Sinus pressure					
Scratchy or itchy throat					
Sore or painful throat					
Difficulty swallowing					
Teary or watery eyes					
Sore or painful eyes					
Eyes sensitive to light					
Trouble breathing					
Chest congestion					
Chest tightness					
Dry or hacking cough					
Wet or loose cough					
Felt nauseous (feeling like you wanted to throw-up)					
Stomach ache					
Felt dizzy					
Head congestion					
Headache					

August 20, 2015 FLU-PRO Version 2.0

Research Tool in Development: Do NOT copy or distribute

Copyright © 2014- 2020 Leidos Biomedical Research, Inc. All Rights Reserved

Please rate the extent to which you had each symptom during the past 24 hours.

	Not at all	A little bit	Somewhat	Quite a bit	Very much
Lack of appetite					
Sleeping more than usual					
Body aches or pains					
Weak or tired					
Chills or shivering					
Felt cold					
Felt hot					
Sweating					

In the past 24 hours, how often have you had any of the following symptoms?

	Never	Rarely	Sometimes	Often	Always
Sneezing					
Coughing					

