APPENDIX 3: DAILY SURVEY

To be completed on D1-10, and D28

FLU-PRO® Plus GLOBAL ADDITIONAL DAILY DIARY ITEMS:

Copyright © 2014- 2020 Leidos Biomedical Research, Inc. All Rights Reserved

Items to be asked in daily diary through to Day 10, and on Day 28 along with the FLU-PRO® symptom items.

1. Overall, how severe were your infection symptoms today? (Please select one response only)

- 0 No flu symptoms today
- 1 Mild
- 2 Moderate
- 3 Severe
- 4 Very severe

2. Overall, how were your infection symptoms today compared to yesterday? (Please select one response only)

- 1 Much better
- 2 Somewhat better
- 3 A little better
- 4 About the same
- 5 A little worse
- 6 Somewhat worse
- 7 Much worse

3. How much did your infection symptoms interfere with your usual activities today? (Please select one response only)

- 1 Not at all
- 2 A little bit
- 3 Somewhat
- 4 Quite a bit

4. Have you returned to your usual activities today?

- 1 Yes
- 0 No

5. In general, how would you rate your physical health today? (Please select one response only)

5 Excellent
 4 Very Good
 3 Good
 2 Fair
 1 Poor

6. Have you returned to your usual health today?

1 Yes
 0 No
 5 Very much

GENERAL DAILY DIARY ITEMS:

1. Have you taken your daily medication as prescribed today?

Yes
 No
 Not applicable

2. Take your vitals: (time of day: _____ : _____ hh:mm)

- Pulse _____ beats per minute
- Temperature _____ °C
- Oxygen saturation level _____ %

3. Have you taken any other medications?

Yes
 No

If "yes", describe: _____

4. Have you observed any change or new complaint since you last completed the survey?

Yes
 No

If "yes", describe: _____

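### Time to sustained symptom resolution has no Day 10 limit, but the symptom diary stops at Day 10 for everyone, so later recovery times are not observed

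*Protocol*

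**What the plan says.** Protocol Section 3 (and the Synopsis) gives the objective "To describe time to symptom resolution in adults with mild COVID-19 treated with molnupiravir compared to placebo" and the endpoint "Time to sustained resolution of symptoms as reported in the Flu-PRO® Plus". The endpoint appears twice among the secondary endpoints, both times without an end day. Other endpoints in the same tables do state one: Day 10 for self-assessed vital signs, and Day 29 for hospitalisation or death and for the maximum WHO score.

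The recording schedule is given in several places:

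- Section 1, footnote l: "The FLU-PRO[®] Plus questionnaire and daily survey will be recorded daily for 10 days by participant". The table itself also marks one completion in the EOS column, Day 29 (±3).
- Section 8.3.1: "The participants will fill in the surveys daily themselves for 10 days".
- Appendix 2 (the FLU-PRO Plus form): "To be completed on D1-10, and D28".
- Appendix 3 (the daily survey): "Items to be asked in daily diary through to Day 10, and on Day 28 along with the FLU-PRO® symptom items".

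Each FLU-PRO Plus item refers to the preceding 24 hours. The additional global items refer to the current day, one of them in comparison with the day before. Staff contacts are scheduled on Days 3, 6 and 10 and then at EOS. No section extends the diary for a participant who is still ill on Day 10, and no scheduled item asks for the date of recovery.

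**The concern.** A time-to-event endpoint needs the event to be datable over the period it covers. A sustained event also needs enough later observations to confirm it. Here the daily record ends on a fixed day whatever the participant's state, and nothing dated follows for 17 days (Days 11-27).

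Two groups are affected. Those still symptomatic on Day 10 have no recovery date. Those who first become symptom-free on the last diary days may have too few remaining entries to show that the resolution lasted.

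The analysis plan may properly define what counts as sustained, and may choose a censoring rule or an interval-censored method. It cannot supply dates that the schedule never collects, so the gap lies in the protocol's data collection. At stake are the later part of the recovery curve in both arms and possibly the median recovery time.

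**Working it through.** **The plan's own figures.** The protocol gives no recovery time, power or sample size for this endpoint. Its one sample-size figure, 1863 per arm for 6% against 4% with 80% power, reproduces exactly (two-sided 0.05 assumed, no continuity correction). This point does not depend on it.

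**Step 1: the observation grid.** Inputs are Section 1 with footnote l, Section 8.3.1 and Appendices 2-3. There are daily forms on Days 1 to 10, none on Days 11 to 27, and one form at about Day 28/29.

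**Step 2: the last datable onset.** Let k be the number of consecutive symptom-free daily forms needed. A run of k forms that ends on Day 10 starts on Day 10 − k + 1 = 11 − k.

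| k | last datable onset |
|---|---|
| 1 | Day 10 |
| 2 | Day 9 |
| 3 | Day 8 |
| 4 | Day 7 |

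Someone ill on Day 10 and well on the Day 28 form has a resolution time known only to lie in (10, 28]. That form covers 24 hours, so it shows current status and not how long the participant has been well.

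**Step 3: other data sources.** The WHO Clinical Progression Scale separates symptomatic from asymptomatic ambulatory patients, but after Day 10 it is scored only at EOS. Adverse event dates do not help either, because Section 9.2.2 keeps fluctuation of mild COVID-19 symptoms out of adverse event reporting. Neither source is FLU-PRO Plus, to which the endpoint is tied.

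**Step 4: illustrative size.** Assumptions that are not in the protocol: exponential resolution times with median m days, k = 3, no missing diaries, and the study-day number used as elapsed time. The share unresolved at day t is S(t) = 2^(−t/m).

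| m (days) | no datable 3-day resolution, S(8) | unresolved at Day 10, S(10) | resolves in the gap, S(10) − S(28) |
|---|---|---|---|
| 5 | 0.330 | 0.250 | 0.229 |
| 7 | 0.453 | 0.371 | 0.309 |
| 9 | 0.540 | 0.463 | 0.347 |
| 12 | 0.630 | 0.561 | 0.363 |
| 14 | 0.673 | 0.610 | 0.360 |

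Counting elapsed time from Day 1 instead (7 days to reach Day 8) changes the first column's range to 2^(−7/5) = 0.379 through 2^(−7/14) = 0.707.

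**Step 5: the median.** The diary reaches the median only if S(11−k) ≤ 0.5, that is, if m ≤ 11−k. With k = 3 the limit is Day 8: a 7-day median is estimable (0.453), a 9-day median is not (0.540).

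**Step 6: effect of continuing the diary.** With daily forms to Day 28, the last datable onset is 29 − k, or Day 26 for k = 3. The undatable share becomes 2^(−26/5) = 0.027 at m = 5 and 2^(−26/14) = 0.276 at m = 14.

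**The case against.** The strongest reply is that a fixed 10-day diary is a reasonable trade between burden and information, for a secondary endpoint whose objective is only to describe, and that nothing is lost from the comparison where data exist. Much of this stands.

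- **Censored participants still count.** Anyone unresolved at Day 10 stays in the risk set until then, so the comparison over Days 1-10 uses all participants with diary data. It can also be well powered. Suppose a hazard ratio of 1.2, 2000 per arm and k = 3. Events by Day 8 are 2000(1 − 2^(−8/m)) + 2000(1 − 2^(−9.6/m)), which is 2321 at m = 7 and 1411 at m = 14. Log-rank power is then 0.992 and 0.928. The hazard ratio is an assumption.
- **Later status is seen.** The symptom form and global items are repeated in both arms at about Day 28, and hospitalisation, death, WHO score and health-care visits run to Day 29. A late difference is not invisible; only its timing is.
- **The definition of sustained may sit in the SAP.** Its absence from the protocol is not the point made here.

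A reader might go further and infer that the endpoint cannot be analysed, that only early recoverers inform the comparison, or that slower recoverers are the higher-risk patients. The first two fail for the reasons above. The third has no source in the protocol, where every participant is high-risk under inclusion criterion 7. Nor can a count of affected participants be quoted as a property of this trial, since no recovery time is given.

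The objection does not answer the mismatch itself. The endpoint is written without a horizon, and recovery after the diary ends is neither dated nor shown to be sustained.

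**Conclusion.** The point holds as a mismatch between the endpoint and its data collection. Resolution needing k consecutive symptom-free diaries is datable only if it begins by Day 11−k. Later resolution is censored at Day 10 or placed only between Day 10 and Day 28. If the true median falls after about Day 11−k, the diary cannot estimate it.

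The one-third to two-thirds range is an illustration that rests on the exponential shape, medians of 5 to 14 days and a three-day rule, none of which comes from the protocol. The existence of the gap rests on none of them.

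The primary endpoint is unaffected, the Day 1-10 comparison is valid and Day 28 status is comparable between arms. This is a worthwhile, inexpensive improvement to a secondary endpoint, not a flaw that undermines the trial.

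**What to change.** In Section 1 footnote l, Section 8.3.1 and Appendices 2-3, state that every participant who has not met the sustained-resolution criterion by the Day 10 diary continues the existing self-completed diary until the criterion is met or the EOS visit. This must include those who first became symptom-free too late for confirmation by Day 10. Otherwise someone who clears on Day 10 would score worse than someone who clears on Day 11. The rule must be identical in both arms, and the late form at about Day 28/29 stays for everyone. The diary needs the value of k in order to stop. Section 10 says that the SAP will be approved before the first enrolment, so the value can be available in time.

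The cost is extra diary burden, and possibly more missing entries, in that subgroup. No visit or procedure is added.

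If this is not adopted, restate the endpoint in the Synopsis and Section 3 as time to sustained resolution within the 10-day diary, with administrative censoring at Day 10, and report Day 28 symptom status separately. This costs only wording, but gives up later recovery times. A recovery date recalled at EOS could be supportive only, because it is not a FLU-PRO Plus measure and depends on memory.

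As an editorial matter in the same edit, mention the EOS completion in footnote l and align the Day 28 label in Appendices 2-3 with EOS Day 29 (±3).
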